The overall objective of this program of research is to improve sexual health outcomes for women diagnosed with breast cancer. Our team is developing a multi-component intervention for the four key predictors of sexual health in female cancer survivors: self-image, vulvovaginal tissue quality and symptoms, desire/energy, and relationship-partner concerns. This proposal begins the proof-of-concept pilot study in women with a history of breast cancer to deliver a multi-component intervention to improve vulvo-vaginal atrophy with a vaginal moisturizer, and sexual energy and self-image with a mind-body intervention that involves relaxation and subconscious suggestions with a hypnotic induction delivered via audio file. The primary outcome will be to evaluate the feasibility and acceptability of a multi-component intervention for sexual function.

1.0 Objectives/Specific Aims

Primary Aim: Evaluate the feasibility and acceptability of a multi-component intervention for sexual function.

Hypothesis: At least 80% of randomized participants will complete the study without differential withdraws from the VVA control group.

Exploratory Aims:

Aim 2: Determine which measure (FSFI, ITS or PROMIS SexF) should be the primary outcome for this multi-component intervention for a larger, well powered randomized trial.

Aim 3: Determine the effect size to be able to adequately power a larger randomized trial.

This study is related to an NCI Moonshot priority (F) to minimize the debilitating side effects of cancer treatment. Completion of these aims will provide a critical foundation for NCI Cancer Prevention and Control Clinical Trials Grant Program R01 submission to implement a phase II or III randomized trial to implement in the NCORP network.

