Perform a hypnotic induction to focus on improving body-image; suggestions for visualizing a body as strong, healthy, and beautiful. Used during study weeks 5 and 6.

Goals:

- Increase relaxation

- Build on positive feelings about your body
- Improve feelings about your sexuality
- Improve sexual experience

Audio III: Hypnotic relaxation for sexual desire and energy

Perform a hypnotic induction to improve desire for intimacy and experience increased energy and sense of wellbeing. Used during study weeks 7 and 8.

Goals:

- Increase relaxation
- Build upon improved feelings about your body
- Build upon improved feelings about your sexuality
- Improve sexual desire and energy

VVA Control

The VVA control group will get the eight weeks of vaginal moisturizer exactly as described above for the intervention group. After completion of the eight weeks of the study, the women assigned to the VVA control will be offered the Hypnotic Relaxation Intervention to complete on their own off study.

Accrual: Our research team has successfully recruited cancer survivors into clinical trials with an average of 4-6 per month. Weekly and monthly accrual goals will be set and achieved through a multipronged recruitment approach.

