7.1 Analysis Plan

Aim 1: Evaluate the feasibility and acceptability of a two-component intervention for sexual function.

Feasibility will be evaluated through determining the accrual rate and screen failures. Acceptability will be determined by retention rates.

Accrual rates will be calculated by determining the number of women per month who consented to participate in the study divided by the number who were eligible and educated about the study.

For purposes of this study, screen failures will be calculated as the number of women for whom full eligibility criteria are evaluated using an eligibility checklist and initial screening call and who are determined to be ineligible through that call.

Retention will be calculated as the number of women who complete all eight weeks of the study and complete the FSFI at baseline and eight weeks divided by the number who are randomized and begin study treatment.

Conversely, attrition rates will be calculated by dividing the number of women who do not provide FSFI endpoint data for all data points by the number of women who are randomized and begin study treatment. Attrition rates of 25% or less will be considered feasible. Withdrawal reasons will be captured and reported by category.

Adherence: Adherence will be determined by calculating the number of women who begin study treatment who have at least an 80% compliance with study treatment related to the vaginal moisturizer and behavioral education materials.

This study will be determined to be feasible and acceptable if we have at least a 60% accrual rate; 80% retention rate and an 80% adherence rate (d+h under adherence).

Aim 2: Determine which measure (FSFI, ITS or PROMISE SexF) should be the primary outcome for this multi-component intervention for a larger, well powered randomized trial.

For all of the patient reported outcome measures, we will calculate missing data rates, change from baseline to each data point, and look at how variable measures are over time. This information, along with effect size data discussed in Aim 3, will be considered in determining the optimal measure to use for the primary outcome in a larger trial.

Criteria we will be looking for in a “winning” measure includes: a lack of missing data on any items; smaller “placebo” response, evidence of a better linear trend over time, and sensitivity to change.

Aim 3: Determine the effect size to be able to adequately power a larger randomized trial.

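### The 80% retention criterion for acceptability pools both arms, so it can be met with the only arm that receives the multi-component intervention at 67–73%

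*Combined protocol and SAP*

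**What the plan says.** Section 1.0 states the aim: "Primary Aim: Evaluate the feasibility and acceptability of a multi-component intervention for sexual function". Its hypothesis is "At least 80% of randomized participants will complete the study without differential withdraws from the VVA control group".

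Section 7.1 says "Acceptability will be determined by retention rates". Retention there is the number of women who finish the eight weeks and give the FSFI at baseline and week 8, "divided by the number who are randomized and begin study treatment". No arm is named. The decision rule reads "This study will be determined to be feasible and acceptable if we have at least a 60% accrual rate; 80% retention rate", and goes on to require 80% adherence on items d and h of section 5.0. Item d is moisturizer use at least 80% of the time. Item h is listening to each audio session more than once a week. The adherence population is women who begin study treatment, again with no arm named. The rule contains no condition on the difference between arms.

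Section 4.4 says of the controls: "The VVA control group will get the eight weeks of vaginal moisturizer exactly as described above for the intervention group". They are offered the audio files only after week 8, off study. The intervention arm has audio sessions three times a week for six weeks and a weekly practice log. Section 7.2 plans 15 women per arm.

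**The concern.** The aim asks whether women accept the two-component treatment. The measure of acceptability averages the arm that receives it with an equally large arm that receives one component and carries less burden. If hypnosis drives women out, good retention among controls can hide it.

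The one phrase that looks like protection, on differential withdrawal, stands in the hypothesis only. It has no margin, test or definition, and the decision rule omits it. Section 1.0 describes completion of these aims as the groundwork for a grant application and a phase II or III trial, so a retention result that does not describe the intervention arm would pass into the planning of that trial.

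**Working it through.** **Inputs.** 15 per arm (7.2); 80% threshold (1.0 and 7.1); moisturizer only for controls on study (4.4). The documents give no expected retention by arm, so the true rates below are assumptions. Section 7.2 gives no calculation behind the 15, so there is no planned figure to reproduce.

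**1. Counts needed.** Pooled: 0.80 × 30 = 24. Intervention arm alone: 0.80 × 15 = 12.

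**2. Splits that give exactly 24 of 30.** These need no assumption about true rates. The last column is the two-sided Fisher exact test between arms.

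| Intervention | Control | Fisher p |
|---|---|---|
| 11/15 (73%) | 13/15 (87%) | 0.65 |
| 10/15 (67%) | 14/15 (93%) | 0.17 |
| 9/15 (60%) | 15/15 (100%) | 0.017 |

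All three meet the pooled criterion. If the differential clause is read as a 5% Fisher test, it stops only the third.

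**3. How often this would happen.** Let Y ~ Bin(15, p_I) be intervention completers and X ~ Bin(15, p_C) be control completers, independent. The pooled criterion is X + Y ≥ 24. The event of interest is X + Y ≥ 24 with Y < 12, summed exactly over the joint distribution. The last row also requires Fisher p ≥ 0.05.

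| Probability | p_I 65%, p_C 95% | p_I 70%, p_C 90% |
|---|---|---|
| Pooled criterion met | 0.61 | 0.61 |
| Intervention arm reaches 12/15 | 0.17 | 0.30 |
| Pooled met, intervention arm below 80% | 0.44 | 0.32 |
| Same, with the Fisher test enforced | 0.25 | 0.25 |

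Over a wider assumed range (control 85–100%, intervention 60–80%), the third row runs from 0.15 to 0.58. With both arms at a true 80%, it is 0.09.

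**4. Strength of the differential clause.** As a 5% Fisher test with 15 per arm, its power at 65% v 95% is 0.40.

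**5. The adherence condition.** Controls have no audio on study, so the effect of item h depends on a denominator that the plan does not state:
- Pooled, controls scored on moisturizer only: 15 controls plus 9 intervention women give 24/30, so controls can carry this criterion too.
- Pooled, item h required of everyone: at most 15/30 = 50%, so the study cannot pass.
- Intervention arm only: 12/15 is needed, which largely blocks a verdict carried by controls.

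**6. Precision and pass rate of an intervention-arm rule.** Exact 95% intervals: 12/15, 52–96%; 24/30, 61–92%. At a true 80%, P(Y < 12) = 0.35 for Bin(15, 0.8), and the pooled rule is missed with probability 0.39 for Bin(30, 0.8).

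**The case against.** A reader might infer that moisturizer-only women can by themselves deliver the overall verdict of feasible and acceptable. The documents do not establish that. The verdict also needs 60% accrual and 80% adherence, including audio listening, and on two of the three readings in step 5 controls cannot carry it. This objection stands and limits the point to the retention criterion. It does not remove the point, because section 7.1 rests acceptability on retention, and the adherence rule leaves its arm unnamed as well.

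The hypothesis does mention differential withdrawal. Enforced as a 5% test, the clause would stop 9/15 v 15/15, so that split is not a fair illustration, and it lowers the 44% and 32% to about 25% each. A descriptive reading might also flag 67% v 93%. But the plan chooses no reading, and the decision rule leaves the clause out.

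Many of the cases counted in step 3 are one woman short. An intervention arm at 11/15 accounts for 0.17 of the 0.44 and 0.18 of the 0.32. To say that the arm would usually be far below 80% would overstate the result. The assumed gaps of 20 to 30 points come from no document.

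Pooled retention also has a proper use. The pilot prepares a randomized trial, and keeping both arms in follow-up is part of whether that trial can be run. That is a reason to report it. It does not make it a measure of how acceptable the combined treatment is.

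**Conclusion.** The concern holds for the retention criterion. As written, the 80% threshold that defines acceptability can be met with 67–73% retention in the only arm that receives the intervention under study, and this follows from the counts alone. How often it would occur rests on assumed rates: 44% of trials at 65% v 95% and 32% at 70% v 90%, or about 25% in each case if the differential clause were applied as a 5% Fisher test. That clause is undefined, missing from the decision rule, and has power of only 0.40 at 65% v 95%.

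The stronger conclusion, that controls can carry the whole verdict, is not supported. It depends on how controls are scored for adherence, which the plan does not say. All calculations assume 15 treated women in each arm and independent outcomes.

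**What to change.** In sections 1.0 and 7.1, apply the 80% retention threshold, and the 80% adherence threshold on items d and h, to intervention-arm women who begin study treatment. That means at least 12 of 15 if the arm has 15. State the rule as a percentage, because section 4.2 describes a random number generator without stated blocking, and the number who start may differ from 15.

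Report control-arm retention, pooled retention and the between-arm difference with confidence intervals, as evidence on the feasibility of running the trial. The reported difference can take the place of the undefined clause in the hypothesis. If the clause is kept as a condition, it needs a definition and a place in the decision rule.

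The change is one of wording. Its cost is precision, since the interval at exactly 80% widens from 61–92% to 52–96%. At a true 80% in the intervention arm, the new rule is missed about 35% of the time. The pooled rule is missed about 39% of the time when both arms are at 80%, so the new rule is not harsher there. It is harder to pass where the intervention arm retains worse than control, which is what the aim is meant to show.

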2.0 Background and Significance

Declines in sexual health in female cancer survivors

By 2030, the number of cancer survivors in the U.S. is expected to grow to nearly 22.1 million.¹ Breast cancer survivors represent almost a quarter of these cases, with the number of survivors at nearly 4 million in 2019 and growing to 5 million by 2030.

The long-term effects that are most strongly linked by evidence to a cancer diagnosis and treatment in female cancer survivors include hot flashes, night sweats, sleep changes, fatigue, and sexual health concerns, including vulvovaginal atrophy (dryness, and dyspareunia), changes in sexual functioning and negative self-image.²⁻⁷ Specific challenges to the sexual response can consist of decreased desire, diminished arousal, decreased ability to achieve orgasm, and pain with vaginal insertion.⁸⁻¹⁰ These physical symptoms can be cumulative and chronic without intervention due to the lack of estrogen and other sex steroid and neuroendocrine hormones. Symptoms associated with estrogen deprivation often contribute to distress, particularly post treatment, as the need to “get back to normal” is prevalent. Difficulties with self-image, mental health, and satisfaction or pleasure often accompany treatment effects creating emotional/psychological stressors.⁹⁻¹¹ Although mixed data exist about the role of relationship issues,^{3,7,10,12,13} the physical and emotional challenges faced by survivors can impact the way a couple communicates and connects with each other as well as how each other’s needs are met.^{14,15} Intimacy can be disrupted, can be put on a hiatus while treatment takes priority or even avoided. Sometimes, without help, the couple may have trouble reconnecting once treatment is completed and life’s routines are trying to return to “normal.”

There is little debate that sexual health concerns and symptoms resulting from the cancer experience have complex etiologies that require education, support and overlapping symptom management.¹⁶ Two recent editorials addressing two clinical trials evaluating pharmacologic interventions for libido (transdermal testosterone and oral bupropion) highlight the importance of developing trials that can simultaneously address factors to promote sexual health within the same study.^{17,18}

To summarize, unlike chemotherapy related side effects like nausea which are transient, the physical effects to a woman’s body, due to hormonal deprivation can be chronic and worsen over time without intervention and have the potential to negatively impact a woman’s emotional adjustment and recovery from cancer. The profound interplay between these physical and emotional concerns/ symptoms necessitates interventions to be designed to address multiple factors simultaneously. Our team has developed a 4-pronged approach to promote sexual health targeting vulvovaginal tissue quality and symptoms, self-image, libido, and partner communication. In this study, we are testing two interventions that together address three of the aforementioned important concerns.

3.0 Preliminary Data

In this section, we will review the existing data for treatment of vulvovaginal atrophy (VVA), libido, and body image. These three components are the focus of this proof-of-concept study.

Vulvovaginal symptoms are consistently identified as predictors of sexual health concerns in female cancer patients and survivors.^{8,19-21} The vagina is highly regulated by estrogen and cancer treatments causing estrogen deprivation result in vulvovaginal dryness and discomfort, bleeding after intercourse, and increased susceptibility to infections, all of which can negatively impact enjoyment and interest in sexual intimacy.²²

Standard/current treatment

The initial treatment for VVA symptoms focuses on non-hormonal treatments to improve tissue quality. Vaginal moisturizers, involving bases such as polycarbophil, hyaluronic acid (HLA), gums or gelatins, may be used on a regular basis for hydrating vaginal tissue. Moisturizers have been shown to stabilize vaginal pH in limited studies and demonstrated efficacy against VVA symptoms.²³ Ospemifene, a Food and Drug Administration-approved selective estrogen receptor modifier (SERM) for dyspareunia, is associated with potential adverse effects including hot flashes and venous thromboembolic events,²⁴ and has not been proven safe for women with breast malignancies. Water- or silicone-based lubricants are also suggested to decrease friction and enhance comfort with sexual touch and activity including vaginal insertion.

The gold standard in the general population if women do not respond to non-hormonal treatment is vaginal estrogen. Initially, the lowest dose possible (eg: 7.5 micrograms [mcg] suppository) is used to provide symptom relief while minimizing systemic effects.^{24,25} Although very low dose vaginal estrogen may not result in systemic concentrations outside of the menopausal range, research has shown significant changes in lipids and bone biomarkers, suggesting systemic effects related to estrogen may indeed occur.^{26,27}

Vaginal estrogens given to women on aromatase inhibitors (AIs) may be absorbed through the vaginal mucosa, resulting in significantly increased circulating levels and systemic effects.²⁸ Therefore for many women with a history of breast cancer, use of low dose vaginal estrogen is a last resort, reserved for when nothing else has been helpful.

In summary, data demonstrates that moisturizers applied to the vagina and vulva can be helpful over time if used frequently enough. A study done by [name] et al. evaluated vaginal DHEA compared to a bioadhesive moisturizer over 12 weeks which found that daily use of a simple moisturizer improved symptoms over 12 weeks with considerable improvement demonstrated by week 4.²³ A study comparing an HLA (non-hormonal) moisturizer to Premarin cream demonstrated significant improvement in both groups by 8 weeks with no difference between the two arms.²⁹ Therefore, we will use a non-hormonal moisturizer to improve the symptoms of vulvovaginal atrophy in this study.

Libido - Energy

There is a lot of controversy in the literature about what constitutes female sexual desire, often called libido.^{30,31} It is clear that sexual desire/libido in women is multifactorial and more complex in comparison to men which appears to be more of a linear relationship between arousal and desire. In women, the relationship is not linear, and is confounded by vulvovaginal health, relationships and self-image.³² It is also likely true that sexual desire may be more challenging in women with a cancer history compared to those without cancer. Specifically, the cancer literature supports that energy (perhaps fatigue) plays an important role in sexual health and declines as a result of a cancer diagnosis and treatment.³³ Data from our recent vaginal Dehydroepiandrosterone (DHEA) study demonstrate that at baseline, vitality explained 13% of overall sexual function (unpublished data). In addition, at baseline, women in our vaginal DHEA study reported vigor/energy levels right around the 50% point (53 out of 100 with higher numbers being better) on the vitality subscale of the Medical Outcomes Scale Short Form-36. Further, linear regression modeling of overall sexual function at baseline found vitality to be a significant predictor ($p=.001$) in addition to the variables of relationship, severity and bother of vaginal symptoms, and chemically induced menopause (unpublished data).

Studies have demonstrated improved libido for women who do not have a history of cancer with use of transdermal testosterone and flibanserin. Flibanserin is a relatively newly approved drug for hypoactive sexual desire disorder in premenopausal women. Studies in female cancer survivors evaluating transdermal testosterone³⁴ and a dopaminergic agent, bupropion,³⁵ have not demonstrated efficacy however. In the recently published bupropion study, baseline and 12-week values for the desire subscale of the FSFI were extremely low in the population of female cancer survivors who participated in this trial, in fact, lower than postmenopausal women diagnosed with hypoactive desire disorder who were included in the flibanserin trials.³⁵ Hence, this area of sexual health remains an important unmet need that will be addressed in this study. We propose to use a behavioral intervention, specifically, hypnosis shown to improve libido outcomes in a previous pilot study.³⁶

Body Image

A comprehensive review of the literature between 1998 and 2010 succinctly summarizes the breadth and complexity of the issues surrounding sexual health in women after a diagnosis of breast cancer. The psychological issues of negative body image, such as feeling sexually unattractive, feeling a loss of femininity, increased anxiety, increased depression, and changes in one's sense of sexual self are noted.¹⁹ A meta-synthesis of 30 qualitative studies representing 795 women supports the concept of "redefining self" in terms of body image and womanhood/femaleness as a pervasive, critical issue in the sexual health and functioning of women with breast cancer.¹¹ Estimates of the prevalence of body image concerns range from 31 to 67%, and the prevalence of those reporting arousal or interest issues is 46 to 56%, respectively.^{11,12,37} Numerous studies, report direct effects on body/self-image in women with a history of breast cancer. In more sophisticated designs, body/self-image has been supported as a predictor of sexual interest and sexual health in general.¹⁰

There are limited, yet sufficient, data to support that psychosocial interventions targeting sexual self/body image are possible and have benefit.³⁸⁻⁴³ In one study, participants were randomized to a 90 minute one-on-one session with a psychologist once a month for three months or to a wait list control to learn and practice mindfulness.³⁹ The intervention group significantly improved post treatment in every domain on the FSFI, except pain. These changes were large enough to be considered clinically important. The control group did not significantly change.³⁹ In a second study, women were randomized to six weekly 2-hour group meetings or to the control group that received printed educational materials. The intervention included education, communication training, and sex therapy. Although the groups did not differ significantly, the women who received the intervention reported greater satisfaction with sex.⁴¹

Our research team recently published a study that evaluated hypnosis versus progressive muscle relaxation for improvements in body image. The primary outcome was the breast impact of treatment scale that measures body change stress.⁴⁴ The study demonstrated that both arms improved significantly on this measure. Hypnotic techniques have a long history of being used for sexual dysfunction and ego/self-esteem strengthening.^{45,46} The objective of the suggestions is to provide women with an improved sense of well-being, health, and positive self-image. In addition, suggestions are given around increasing ones' sense of control and the ability to manage physical and mental tension that have resulted in fatigue and apathy regarding sexual activity.⁴⁵ Imagery techniques can assist women in attaining, or re-attaining, a positive view of their sexual self. We will be using our hypnotic intervention from our previously published study in this two-component trial. Suggestions for sexual desire and energy will be integrated into the hypnosis in order to address both issues within one behavioral intervention.

Summary

This proof-of-concept study is the first step toward developing a well powered randomized clinical trial to evaluate the efficacy of a two-component intervention on three critical predictive variables of sexual function. This study intends to demonstrate a proof of concept that we can implement a two-step approach to address three areas of sexual function after cancer diagnosis and treatment: VVA, body image changes, and sexual desire/energy. All women will receive the same treatment for their VVA, and then be randomized to either arm 1: receiving hypnosis for body image and sexual desire after two weeks of VVA treatment or arm 2: VVA control group. The VVA control group will have the option to receive the hypnosis intervention after completion of eight weeks of the VVA treatment.

The potential for a comprehensive approach to sexual health improvement

This program of research builds upon work done by Ganz and colleagues.^{4,5,9} They designed a comprehensive menopausal assessment intervention to address three symptoms (hot flashes, vaginal dryness, and urinary incontinence). Advanced practice nurses assessed each woman's needs and developed a tailored intervention including pharmacologic and behavioral interventions for these three main issues. At the time of this study, there was a paucity of effective interventions for these problems. Despite this, the investigators report significant improvements in sexual health as measured by the sexual summary scale from the Cancer Rehabilitation Evaluation System (CARES) in comparison to the usual care control group. The improvements were sustained at the two month follow up.⁹ We are building on this multi-symptom, individualized approach, endorsed as a reasonable approach by others⁴⁷ and will target the three important symptoms shown to impact sexual health, specifically vulvovaginal atrophy, self-image, and sexual desire in this one proof of concept study.

The Team

[name] [name], FAAN is a recognized expert in oncology symptom management and Vice Chair of the Cancer Control committee in NRG Oncology. [name] has had a rigorous program of research in the area of sexual health in cancer survivors. She has developed and implemented two clinical trials for libido (transdermal testosterone³⁴ and bupropion³⁵ and one for vulvovaginal atrophy²³ in the NCORP setting, involving multiple sites and hundreds of participants. [name] will retire December 31, 2024.

